#### **8.4.3. Clinical Global Impression of Improvement (CGI-I)**

The CGI-I will be assessed by the Investigator at Weeks 12, 16, 20, and 24, in Part A Period 1 only. Compared to the patient’s alopecia areata prior to treatment at baseline, the patient’s current state of alopecia areata will be assessed according to the Investigator’s perceived change. The Investigator may select one of seven numeric choices representing “Very Much Worse” to “Very Much Improved”. To reduce variability, one rater should perform the CGI-I assessment for the patient for the duration of the study. An example of the CGI-I assessment can be found in Appendix 18.3.2 of the protocol.

The percentage of responders (defined as “much improved” or “very much improved”) using the CGI-I at Weeks 12, 16, 20, and 24 will be assessed per Section 8.4 in Part A Period 1 only. No missing data will be imputed for this endpoint.

#### **8.4.4. Clinical Global Impression of Severity (CGI-S)**

The CGI-S will be assessed by the Investigator and will consider the severity of the patient's alopecia areata at the time of assessment. The Investigator may select one of seven numeric choices representing "Among the most extreme hair loss" to "Normal, no hair loss". To reduce variability, one rater should perform the CGI-S assessment for the patient for the duration of the study. An example of the CGI-S assessment can be found in Appendix 18.3.1 of the protocol.

The continuous secondary endpoint of change from baseline in the CGI-S at Weeks 12, 16, 20, and 24 will be assessed per Section [8.4](#) in Part A Period 1 only. No missing data will be imputed for this endpoint.

#### **8.4.5. Patient Global Impression of Improvement (PGI-I)**

The PGI-I will be assessed by the patient at Weeks 12, 16, 20, and 24 in Part A Period 1 only. Compared to the patient's alopecia areata prior to treatment at baseline, the patient's current state of alopecia areata will be assessed according to his/her perceived change. The patient may select one of seven numeric choices representing "Very Much Worse" to "Very Much Improved". An example of the PGI-I assessment can be found in Appendix 18.3.4 of the protocol.

The secondary PGI-I responder endpoint of percentage of responders (defined as "much improved" or "very much improved") at Weeks 12, 16, 20, and 24 will be assessed per Section [8.4](#) in Part A Period 1 only. No missing data will be imputed for this endpoint.

#### **8.4.6. Patient Global Impression of Severity (PGI-S)**

The PGI-S will be assessed by the patient and will consider the severity of his/her alopecia areata at the time of assessment. The patient may select one of seven numeric choices representing "Among the most extreme hair loss" to "Normal, no hair loss". An example of the PGI-S assessment can be found in Appendix 18.3.3 of the protocol.

The continuous secondary endpoint of change from baseline in the PGI-S at Weeks 12, 16, 20, and 24 will be assessed per Section [8.4](#) in Part A Period 1 only. No missing data will be imputed for this endpoint.

#### **8.4.7. Quality of Hair Patient Reported Outcome (QPRO)**

The QPRO questionnaire is a 4-item assessment which provides additional details on key attributes of patient hair and helps provide context to the SPRO response. Like the SPRO, the QPRO responses are on a scale of 1-5, where 1 = very satisfied, 2 = satisfied, 3 = neither satisfied nor dissatisfied, 4 = dissatisfied, and 5 = very dissatisfied. An example of the QPRO assessment can be found in Appendix 18.4.2 of the protocol.

The continuous secondary endpoints of change from baseline for each individual item of QPRO at Weeks 12, 16, 20, and 24 will be assessed per Section [8.4](#) in Part A Period 1 only. No missing data will be imputed for this endpoint.

## 8.5. Other Endpoints

### 8.5.1. Time to First LOM (Part A only)

Time to first LOM (in weeks) will be summarized descriptively with Kaplan-Meier methodology for patients in the Efficacy Population who entered Part A Period 2. Treatment sequence across Period 1 and Period 2 (8 mg BID to 4 mg BID, 8 mg BID to placebo, 12 mg BID to 8 mg BID, and 12 mg BID to placebo) will be used as strata to present quantiles (25%, median, 75%), if estimable. Ninety-five percent confidence intervals for the median will be presented, if estimable, using the Brookmeyer and Crowley (1982) method. If KM statistics are not estimable, standard descriptive statistics for non-censored patients will be displayed.

First LOM is defined as the first date where a patient has an absolute SALT score  $>20$  in Part A Period 2. Time in weeks will be calculated from the date of randomization in Part A Period 2, as

- (date of first LOM (or censored date) - date of Part A Period 2 randomization + 1)/7

Patients who do not experience LOM before completion of Part A Period 2 or otherwise prematurely discontinue from Part A Period 2 will be censored at their last study visit date where SALT was measured in Part A Period 2 of the study, or a maximum of 24 weeks.

A Kaplan-Meier plot over time will also be presented.

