Patients in Part A, Period 2 will stay on their assigned dose for a maximum of 24 weeks or until they meet the criteria for loss of regrowth maintenance (LOM), defined as an absolute SALT score >20. Any patient meeting the LOM criteria at any assessment timepoint during Part A, Period 2 will enter Part B of the study and return to their original CTP-543 treatment from Part A, Period 1 (8 mg BID or 12 mg BID). Patients not meeting the LOM criteria (e.g., their absolute SALT score remains \leq 20) at the end of 24 weeks will have the opportunity to continue receiving treatment in the Open-Label Extension study (CP543.5001) or they will complete treatment at Week 24 and return in 4 weeks for the Post-Treatment Safety Follow-up.

Assessment of treatment response using SALT for efficacy will occur at 4, 8, 12, 16, 20 and 24 weeks. The primary efficacy analysis will be conducted when all patients have completed Week 24 of Part A, Period 2. The study design is depicted below.

Part A: Treatment and Dose Modification Phase

Part B: Re-Treatment Phase

Part B: Re-

Figure 2: CP543.2004 Study Design

LOM: Loss of Maintenance

Part B (Re-Treatment Phase)

Any patient from Part A, Period 2 meeting the LOM criteria (SALT > 20) will enter into Part B of the study and return to their original 8 mg BID or 12 mg BID dose assigned in Part A, Period 1. Patients will stay on their assigned dose for 24 weeks regardless of whether they meet the criteria for Restoration of Regrowth (ROR) or not. ROR is defined as the patient's attainment of an absolute SALT score ≤20. Assessment of treatment response using SALT for efficacy will occur monthly during the 24-week period. Patients will have the opportunity to continue receiving treatment in the Open-Label Extension study (CP543.5001) or they will complete treatment at Week 24 and return in 4 weeks for the Post-Treatment Safety Follow-up.

Safety

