13.1. Sample Size Rationale

Approximately 300 patients will be randomized for Part A, Period 1 of the study. Allocation to each of the dose groups will be slightly imbalanced (approximately N= 170 for 8 mg BID and N= 130 for 12 mg BID) to attempt to get approximately 50 Responders per dose group to enter the Period 2 dose modification Phase. It is anticipated that there will be approximately 25 patients in each dose reduction and drug discontinuation arm for each dose group in Period 2. A sample size of 25 patients per arm should be adequate for describing the effects of dose modification in patients previously experiencing hair regrowth.

There is no formal hypothesis testing and consequently sample size was not based on power calculations.

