13.4.2. Efficacy

All efficacy summaries will be descriptive with no statistical hypothesis testing and based on the Efficacy Population. Time to LOM will be summarized descriptively with Kaplan-Meier methodology. Patients who do not experience LOM before completion or premature discontinuation from Part A will be censored at their last study visit in Part A.

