original collected data. The mean and median will be reported to an additional level of precision than the original observations, and the standard deviation will be reported to two additional levels of precision than the original observations. The precision for some original collected data and derived variables are longer than required for clinical interpretation (eg, >15 decimals). In these situations, the number of decimal places will be determined by the table of precision included as an attachment.

All efficacy summaries are descriptive with no statistical hypothesis testing. Confidence intervals and estimated treatment differences will be rounded to one additional decimal place from the original data, or a maximum of two decimal places. Standard error will be reported to an additional level of precision. Results which cannot be determined will be displayed as “NA”, “NE”, or similar.

Treatment start date for each part and period will be defined as the date of randomization or re-randomization for the respective part or period. If the treatment start date for Part A Period 2 is equal to the treatment end date for Part A Period 1 as collected on the eCRF, it will be assumed that the treatment day is associated with Part A Period 2. One day will be subtracted from the treatment end date for Part A Period 1. Similarly, if the treatment start date for Part B is equal to the treatment end date for Part A Period 2, it will be assumed that the treatment day is associated with Part B. One day will be subtracted from the treatment end date for Part A Period 2.

Date of last dose is collected on the *Treatment Discontinuation/Completion* eCRF page for each part/period. For patients with missing or partial date of last dose, or for patients who are ongoing at the time of the NDA submission, the date of last dose (ie, treatment end date) will be imputed. Date of last dose will be imputed as follows:

- For entirely missing dates for patients who are not ongoing or for partial dates where the month and day are missing, date of last dose will be imputed as the last visit date that is not a follow-up visit within a period or part.
- For partial dates where only the day is missing, the day will be imputed as the last day of the month. If this imputed date is after the treatment start date of the next part or period, or the study discontinuation date of that part or period, the day will be imputed to one day before the treatment start date of the next part or period.

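### When Kaplan-Meier quantiles for time to LOM cannot be estimated, SAP 8.5.1 displays times for only the patients who lost regrowth, a figure that understates durability and is not comparable across arms

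*SAP*

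**What the plan says.** Protocol 13.4.2 plans the analysis in one line, "Time to LOM will be summarized descriptively with Kaplan-Meier methodology", with patients who do not reach LOM censored. It has no alternative for quantiles that are not reached.

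SAP 8.5.1 adds the detail. The four treatment sequences are "used as strata to present quantiles (25%, median, 75%), if estimable", and the median gets a 95% confidence interval on the same condition. It then adds: "If KM statistics are not estimable, standard descriptive statistics for non-censored patients will be displayed". Time in weeks is ("date of first LOM (or censored date) - date of Part A Period 2 randomization + 1)/7". Patients without LOM are censored at their last visit with a SALT measurement "in Part A Period 2 of the study, or a maximum of 24 weeks". A Kaplan-Meier plot is also planned.

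SAP 4 has a general convention, "Results which cannot be determined will be displayed as" NA, NE or similar, but also says that rules in a specific section override the general ones. SAP 13 does not list the fallback as a change from the protocol. SAP Appendix 15.4 marks the time-to-LOM table (Table 14.2.4.1) for the abbreviated report that supports the NDA.

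**The concern.** A Kaplan-Meier median is not reached when fewer than half of an arm loses regrowth during follow-up. For a dose-reduction arm that is the favourable result. The fallback then describes only the minority who lost hair. Because Period 2 lasts 24 weeks, their times cannot exceed about 24 weeks however few of them there are, so the figure carries no information on how many patients kept their regrowth.

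Two different quantities can then stand under one table title: quantiles that use all patients in arms with many losses, and times conditional on loss in arms with few. The SAP asks for no label to tell them apart. Someone reading across the columns could conclude that a well-maintained arm lost hair early.

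**Working it through.** **Inputs.**
- Protocol 13.1 sets the allocation "to attempt to get approximately 50 Responders per dose group". Protocol 8.3 re-randomises responders 1:1 in Period 2, so 50 / 2 = 25 per arm. This reproduces the plan's figure of about 25.
- SALT visits, Protocol 8.1: "Assessment of treatment response using SALT for efficacy will occur at 4, 8, 12, 16, 20 and 24 weeks".
- LOM rates: the documents give none. Rates of 20% to 90% by Week 24 are assumed here, with a constant chance of loss at each of the six visits and no early dropout.

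**Step 1: losses needed for each quantile, n = 25.** The curve must fall to 0.75, 0.50 or 0.25.
- 25% quantile: 7 losses (18/25 = 0.72; with 6 losses, 19/25 = 0.76).
- Median: 13 losses (12/25 = 0.48).
- 75% quantile: 19 losses (6/25 = 0.24).

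**Step 2: chance that a quantile is missing.** This is the probability that a Binomial(25, p) count is at most 6, 12 or 18. It treats the Week 24 visit as one time point for losses and censoring (see Step 5).

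| True LOM by Week 24 | 25% quantile missing | Median missing | 75% quantile missing |
|---|---|---|---|
| 20% | 78% | 100% | 100% |
| 30% | 34% | 98% | 100% |
| 40% | 7% | 85% | 100% |
| 60% | 0% | 15% | 93% |

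If every quantile must be missing, the first column gives the chance that the fallback applies. If one missing quantile is enough, the last column does, and almost every arm up to 60% LOM is affected.

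**Step 3: what the fallback displays.** The loss probability per visit is h = 1 − (1 − p)^(1/6), which is 0.0365, 0.0577 and 0.0816 at p = 20%, 30% and 40%. A loss at visit k has conditional probability h(1 − h)^(k−1) / p.
- Mean time among losers, visits at exactly 4, 8, …, 24 weeks: 13.6, 13.3 and 13.0 weeks, with median 12.
- The SAP formula adds one day, or 1/7 = 0.14 week, giving about 13.7, 13.5 and 13.2 weeks, with median 12.1.
- In all three arms the true median is beyond 24 weeks.

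**Step 4: Kaplan-Meier medians in arms with more losses.** The proportion without LOM after visit k is (1 − p)^(k/6). The median is the first visit at which this is 0.50 or less.
- p = 60%: 0.543 at Week 16, 0.466 at Week 20; median about 20 weeks.
- p = 70%: 0.548 at Week 12, 0.448 at Week 16; median about 16 weeks.
- p = 80%: 0.585 at Week 8, 0.447 at Week 12; median about 12 weeks.
- p = 90%: 0.681 at Week 4, 0.464 at Week 8; median about 8 weeks.

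Against the 60% or 70% arm, a 20–40% arm shown at 13 to 14 weeks appears to lose hair sooner. Against the 80% arm the medians tie at 12, and against the 90% arm the order is right.

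Timing matters too. Take 5 losses among 25. With 2 at Week 8, 2 at Week 12 and 1 at Week 16, the displayed mean is (2×8 + 2×12 + 16)/5 + 0.14 = 11.3 weeks. With 2 at Week 20 and 3 at Week 24, it is (2×20 + 3×24)/5 + 0.14 = 22.5 weeks.

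**Step 5: the censoring cap.** An on-schedule Week 24 visit is day 169, and 169/7 = 24.14 weeks. A patient with LOM at that visit has time 24.14, while a patient without LOM is capped at 24 and leaves the risk set first. In the late-loss example the curve is 23/25 = 0.92 after Week 20. At 24.14 weeks only the 3 losers remain, so it falls to 0.92 × (1 − 3/3) = 0. With the 20 maintained patients still at risk it would be 0.92 × (1 − 3/23) = 0.80. Taken literally, the cap can make quantiles falsely estimable at 24.14 weeks, and an estimate read at exactly 24.0 weeks would miss the Week 24 losses.

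**The case against.** The strongest reply is that little depends on this table. Time to LOM is listed in the SAP under other endpoints. The co-primary analyses are the percentages with and without LOM per arm, and the study is descriptive with no hypothesis tests. The Kaplan-Meier plot and the co-primary table are marked for the same abbreviated report, and the SAP's standard descriptive statistics include the number of patients. A careful reader would see how few losses lie behind the figure. All of this stands and limits the harm, but it does not make the displayed figure right.

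Second, the fallback may be meant only for arms in which no quantile can be estimated, and it says that statistics are displayed, not that they replace an NE entry. Both readings are possible. The text settles neither, and no table shells are available to show the layout. Even the narrow reading applies 78% of the time at 20% LOM.

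Third, a reader might infer that the rule always makes the better-maintained arm look worse. The documents do not support that: they give no LOM rates or timing, and the reversal disappears against an arm with 80% LOM or when the few losses come late. If one missing quantile is enough, a 60% arm would usually show events-only times as well (mean 12.4 weeks against 13.7 at 20% LOM), which hides the difference rather than reversing it.

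**Conclusion.** The concern holds as a defect in a reporting rule. For any arm in which fewer than half lose regrowth, the events-only figure understates a median that lies beyond 24 weeks, and it is a different quantity from the Kaplan-Meier quantiles of other arms. This needs no assumption about hazard, only that follow-up is largely complete. The 13 to 14 weeks shown against medians of 20 or 16 weeks rests on assumed LOM rates, constant loss per visit, 25 per arm and no early dropout. Reversal of order is possible, not general.

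It would go too far to treat time to LOM as the trial's main durability measure, or to say that a primary result is wrong. The co-primary percentages do not depend on this rule. What is at stake is a misleading entry in a table of a report that supports the NDA. The cap in Step 5 is a separate flaw in the same section and has to be corrected with it, or the repaired table will still be wrong at Week 24.

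**What to change.** Amend SAP 8.5.1 and Table 14.2.4.1 before the database freeze for the abbreviated report:

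1. Delete the events-only fallback. If it is kept, give it its own row in all four arms, labelled: among patients with LOM, n events/N.
2. Show each quantile that is not reached as NE (not reached by Week 24), quantile by quantile and arm by arm. This also removes the ambiguity about the trigger.
3. For all four arms, add the Kaplan-Meier percentage without LOM at the Period 2 Week 12 and Week 24 visits, with 95% confidence intervals.
4. Align the cap with the Week 24 visit, including its ±2-day window (up to 171/7 = 24.43 weeks). One way is to use the nominal visit week for both losses and censoring. LOM found at that visit must count, and patients without LOM there must stay in the risk set until it.

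The cost is one sentence removed or reworded, one censoring clause changed, and two rows added to an existing table. No new data are needed.

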Event	Day -28 to Day -1 (Visit 1)	Randomization ^{1, 2} Day 1 (Visit 2)	Week 2 (Visit 3)	Week 4, 8 (Visit 4, 5)	Week 12 (Visit 6)	Week 16, 20 (Visit 7, 8)	Week 243,4 (Visit 9)	Week 28 ⁵ (Visit 10)	Week 32 (Visit 11)	Week 36 (Visit 12)	Week 40, 44 (Visit 13, 14)	Week 484 (Visit 15)	Safety Follow-Up Visit
Informed consent	X												
Eligibility assessment	X	X											
Demographics	X												
Medical history	X	X											
Randomization		X					X^7						
PE	X	X					X					Х	X
Brief PE				X	X	X			X	X	Х		
Height	X												
Weight	X	X		X	X	X	X		X	X	X	X	X
Pregnancy test ⁸	X	X ⁹		X	X	X	X	X	X	X	X	X	
Tuberculosis test	X												
Clinical laboratory testing ¹⁰ , 11	X ¹²	X	X	X	X	X	X	X	X	X	X	X	X
Lipid assessment ¹³		X			X		X			X		X	X
HBV and HCV test	Х												
12-lead electrocardiogram	Х	X			Х		X			X		Х	X
Vital signs	X	X		X	X	X	X		X	X	Х	X	X
SALT assessment	Х	X		X	X	X	X	X^{14}	X^{14}	X^{14}	X14	Х	
Photographs	X	X		X	X	X	X	X	X	X	Х	X	
SPRO and QPRO		X			X	X	X						
CGI-S and PGI-S		X			Х	X	X						
CGI-I and PGI-I					X	X	X						
Dispense study drug		X		X	X	X	X^7	X^{15}	X^{15}	X^{15}	X15		
Pharmacokinetic blood sampling ¹⁶		X			X		X						
Study drug accountability				X	X	X	X		X	X	X	X	_
Adverse events	X				X					X			X
Concomitant medications	X		X			X				X			

PE = Physical Examination; HBV= hepatitis B virus; HCV = hepatitis C virus; SPRO = Satisfaction of Hair Patient Reported Outcome; QPRO = Quality of Hair Patient Reported Outcome; CGI-S = Clinical Global Impression of Severity; CGI-I = Clinical Global Impression of Improvement; PGI-S= Patient Global Impression of Improvement; PGI-I = Patient Global Impression of Improvement;

- ¹ Day 1 (Visit 2) may occur any time after Screening laboratory results are available and reviewed by the Investigator.
- ² For Part A, Period 1, all subsequent visits and week increments should be based on the date of Visit 2. All visit windows are ± 2 days.
- ³ Week 24 from Part A, Period 1 will also serve as the Day 1 visit for Part A, Period 2 for those who meet criteria to continue into the Dose Modification Phase.
- ⁴ Also serves as the Early Termination Visit for patient withdrawal in this period.
- ⁵ For Part A, Period 2, all subsequent visits and week increments should be based on the date of Week 24 (Visit 9). All visit windows are ±2 days.

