#### 8.1.2. Assessment Time Windows

The visit schedule for all study assessments is provided in Appendix 15.2, by Part. For scheduled visits, there will be no reassignment of the analysis visit based on date. Unscheduled visits and early termination visits will be reassigned based on the analysis windows in the below table and the schedule of events. Assessments in part B will be windowed counting from the part B treatment start date. Assessments may only be re-assigned to visits where they were to be collected per the schedule of events. The latest assessment in a window will be selected as the visit used in summaries, unless otherwise specified. All visits will be included in by-patient data listings.

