**Table 2: Analysis Windows for Unscheduled and Early Termination Visits**

	Nominal Visit	Safety Analyses			Efficacy Analyses		
		Lower	Target	Upper	Lower	Target	Upper
Part A, Period 1	Screening	-28	-1	-1	-28	-1	-1
	Visit 2-Randomization	1	1	1	1	1	1
	Visit 3-Week 2	2	15	22	12	15	18
	Visit 4-Week 4	23	29	43	26	29	32
	Visit 5-Week 8	44	57	71	54	57	60
	Visit 6-Week 12	72	85	99	82	85	88
	Visit 7-Week 16	100	113	127	110	113	116
	Visit 8-Week 20	128	141	155	138	141	144
Part A, Period 2	Visit 9-Week 24	156	169	183	166	169	172
	Visit 10-Week 28 (PAP2 Week 4)	184	197	211	194	197	200
	Visit 11-Week 32 (PAP2 Week 8)	212	225	239	222	225	228
	Visit 12-Week 36 (PAP2 Week 12)	240	253	267	250	253	256
	Visit 13-Week 40 (PAP2 Week 16)	268	281	295	278	281	284
	Visit 14-Week 44 (PAP2 Week 20)	296	309	323	306	309	312
	Visit 15-Week 48 (PAP2 Week 24)	324	337	351	334	337	340
Part B	Visit B1-Day 1	1	1	1	1	1	1
	Visit B2-Week 2	2	15	22	12	15	18
	Visit B3-Week 4	23	29	43	26	29	32
	Visit B4-Week 8	44	57	71	54	57	60
	Visit B5-Week 12	72	85	99	82	85	88
	Visit B6-Week 16	100	113	127	110	113	116
	Visit B7-Week 20	128	141	155	138	141	144
	Visit B8-Week 24	156	169	183	166	169	172

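### SAP 8.5.1 caps censoring times at 24 weeks but not LOM times, so one LOM at Period 2 Week 24 can take the Kaplan-Meier curve to zero

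*SAP*

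**What the plan says.** SAP 8.5.1 defines the event by calendar date: "First LOM is defined as the first date where a patient has an absolute SALT score" above 20 in Part A Period 2. Event and censoring times share one formula, "date of first LOM (or censored date) - date of Part A Period 2 randomization + 1)/7". Patients without LOM are censored at their last visit "where SALT was measured in Part A Period 2 of the study, or a maximum of 24 weeks". That limit stands only in the sentence on censored patients. The four treatment sequences "will be used as strata to present quantiles (25%, median, 75%), if estimable", with a confidence interval for the median and a Kaplan-Meier plot.

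The protocol has no limit. Under Protocol 13.4.2, patients without LOM "will be censored at their last study visit in Part A". SAP 13, as far as its published list shows, does not record the limit as a change.

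On the schedule, Protocol Table 1, footnote 5 says that Period 2 visits "should be based on the date of Week 24 (Visit 9). All visit windows are ±2 days". SAP Table 2 gives the row "Visit 15-Week 48 (PAP2 Week 24") a target of Day 337, against Day 169 for Visit 9, where Period 2 randomization takes place. SAP 8.4.1 counts LOM at Period 2 Week 24.

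**The concern.** Patients who maintain regrowth and patients found to have LOM at the last visit are seen on the same days. A Kaplan-Meier estimate has to keep the maintained patients in the risk set when those last LOMs are counted. A limit on censoring times alone moves the maintained patients ahead of the LOMs. The risk set at the last event then holds only LOM patients, and the product-limit estimate becomes 0 however many patients maintained.

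The affected outputs are Table 14.2.4.1 and Figure 14.2.4.1, both marked for the abbreviated NDA report. An arm in which most patients kept their hair could show a curve ending at zero and a median of about 24 weeks where the correct entry is not reached. The error has one direction: it overstates loss of maintenance. It would also contradict the co-primary percentages in the same report.

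**Working it through.** The plan states no figure to reproduce here. Its schedule is consistent with itself: 1 + 24×7 = 169, 1 + 48×7 = 337, and 337 − 169 = 168 days.

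**Times at Period 2 Week 24.** The SAP 8.5.1 formula, (days since randomization + 1)/7, over the ±2-day window:

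| Days since randomization | 166 | 167 | 168 | 169 | 170 |
|---|---|---|---|---|---|
| Weeks | 23.86 | 24.00 | 24.14 | 24.29 | 24.43 |

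**Two readings of the limit on censored patients.**

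1. It applies to the week value. Maintained patients are censored at 24.00 or earlier. A LOM on days 168, 169 or 170 comes after all of them.
2. It applies to the date, randomization + 168 days. Maintained patients are censored at 24.14 or earlier. A LOM on day 168 is then handled correctly, because tied censored patients stay in the risk set. A LOM on day 169 or 170 still comes after all of them.

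**Worked example (assumed data).** An arm of 25 has one LOM at each of Weeks 4, 8, 12, 16 and 20, one at Week 24, and 19 maintained patients seen on day 168. Before Week 24, S = 20/25 = 0.80.

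- Scheduled weeks: S = 0.80 × (1 − 1/20) = 0.76. None of the three quantiles is reached.
- Week 24 LOM on day 168, reading 1: risk set 1, S = 0.80 × (1 − 1/1) = 0, and all three quantiles are 24.14 weeks. Reading 2: S = 0.76.
- Week 24 LOM on day 169: S = 0 under both readings, and all three quantiles are 24.29 weeks.

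**How often.** Assumptions: the planned 25 per arm (Protocol 13.1), constant hazard over the six visits, visits uniform over the five window days, no dropout. The true 24-week LOM rate p is not in the documents and is varied. The chance that a patient's first LOM is at Week 24 is d = (1−p)^(5/6) − (1−p). The curve falsely reaches 0 if at least one such LOM is on a late day, so P = 1 − (1 − d·q)^25, with q = 3/5 (reading 1) or 2/5 (reading 2). The false-median columns come from simulation of 20,000 arms per scenario. They count arms where a median is reported although the scheduled-week estimate has none.

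| p | d | False zero, reading 1 | False zero, reading 2 | False median, reading 1 | False median, reading 2 |
|---|---|---|---|---|---|
| 20% | 0.0303 | 36.8% | 26.3% | 36.2% | 26.2% |
| 30% | 0.0429 | 47.9% | 35.1% | 46.3% | 34.4% |
| 50% | 0.0612 | 60.8% | 46.2% | 28.0% | 23.0% |

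The same simulation gave false zeros of 36.3%, 47.5% and 61.2% (reading 1) and 26.2%, 35.0% and 46.7% (reading 2), in line with the formula.

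**Deleting the limit but keeping actual dates.** Maintained patients seen early in the window still leave before LOMs seen later in it. At p = 20%, 30% and 50%, false zeros fall to 0.2%, 0.5% and 2.2%. The mean final estimate is 0.764, 0.650 and 0.435 against 0.80, 0.70 and 0.50 on scheduled weeks, and it is more than 10 points off in 12%, 17% and 24% of arms.

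**The case against.** The limit may have been meant for every patient. A 24.00-week limit on LOM and censoring times alike gives no false zeros at p = 20%, 30% or 50%, and false medians in only about 0%, 1% and 3% of arms. That would be a smaller repair that keeps actual dates. The performance is real, but SAP 8.5.1 does not say this, so a text change is needed in either case. One could also argue that a LOM found at the completion visit does not come before completion and should be censored. That would discard events which the SAP's own LOM definition and SAP 8.4.1 count.

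The size depends on assumptions, and this stands. If LOM comes early, with say 3% of events at Week 24, then at p = 50% d = 0.015 and reading 1 gives 1 − (1 − 0.009)^25 = 20% instead of 61%. In arms with high LOM, as the placebo arms may be, the median is largely safe: under reading 1 a false median occurs in about 1% of arms at p = 70% and none at 80%. What remains there is mainly a wrong tail. With 18 early LOMs, 1 at Week 24 and 6 maintained, the median stays at 12.14 weeks but the curve ends at 0 instead of 0.24.

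The departure from the protocol is a minor matter: the protocol leaves details to the SAP, the SAP claims primacy, and a figure next to the SAP 13 list is not shown. It is also true that this is a descriptive endpoint listed under other endpoints, and that a curve at zero beside the co-primary table would look odd enough to be questioned.

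**Conclusion.** The concern holds. As written, the rule fails under both readings of the limit on censored patients. A single LOM at Period 2 Week 24 is enough if it is dated on or after the target day (week reading) or after it (date reading); a LOM seen one or two days early does no harm. Under the stated assumptions, about a quarter to three fifths of arms would show a false zero for LOM rates of 20% to 50%, and fewer if LOM clusters early. The median is most exposed in arms where most patients maintain, which is where it should read not reached. The co-primary and by-visit LOM percentages do not use this clock and are unaffected. It should be fixed before the analysis for the abbreviated report is run, but it does not threaten the main result.

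**What to change.** Time both LOM and censoring by scheduled Period 2 week in SAP 8.5.1 and delete the 24-week limit. Suggested text:

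> Time to first LOM is the scheduled Period 2 week (4, 8, 12, 16, 20 or 24) at which SALT >20 is first recorded. Patients without LOM are censored at the scheduled week of their last Period 2 SALT. An unscheduled or early-termination SALT outside the Table 2 efficacy windows counts at the next scheduled week if it shows LOM (Week 24 if it falls after the Week 24 window), and otherwise at the last scheduled week with a SALT (week 0 if there is none).

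The last sentence is needed because the efficacy windows leave 21 uncovered days between successive Period 2 visits, for example Days 173 to 193. Table 2 numbers the Period 2 windows on the Period 1 day count, so the text should also say that they are applied from the actual Period 2 randomization date.

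Scheduled visits need no new rule, since SAP 8.1.2 already states: "For scheduled visits, there will be no reassignment of the analysis visit based on date". If the team prefers actual dates, the minimum repair is to state that one 24.00-week limit applies to LOM and censoring times alike, at the price of a small remaining ordering error within the visit window.

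The cost is a few sentences in SAP 8.5.1, one line in SAP 13 and matching code. Data collection and conduct do not change. Day-level timing is lost, which matters little when LOM is detected only at 4-weekly visits.
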